- Vapometer: transepidermal water loss (TEWL) on both cheeks will be measured at T0 (baseline), T14d (after pre-treatment), T15d (Timm post-procedure), T16d (1-day after self-recovery), T18d (3-day after self-recovery), T22d (7-day after self-recovery), T25d (10-day after self-recovery and product treatment start), T32d (7-day after product treatment), T39d (14-day after product treatment) for all groups.
- **Cutometer:** skin elasticity (R2, R5, R7) on both cheeks will be measured at T0 (baseline), T14d (after pre-treatment), T15d (Timm post-procedure), T16d (1-day after self-recovery), T18d (3-day after self-recovery), T22d (7-day after self-recovery), T25d (10-day after self-recovery and product treatment start), T32d (7-day after product treatment), T39d (14-day after product treatment) for all groups.
- **pH-meter:** skin pH value on both cheeks will be measured at T0 (baseline), T14d (after pre-treatment), T15d (Timm post-procedure), T16d (1-day after self-recovery), T28d (3-day after self-recovery), T22d (7-day after self-recovery), T25d (10-day after self-recovery and product treatment start), T32d (7-day after product treatment), T39d (14-day after product treatment) for all groups.

Photo Capture and Imaging Analysis(N=60):

- VISIA 7: standard facial photos shooting will be done at T0 (baseline), T14d (after pre-treatment), T15d (Timm post-procedure), T16d (1-day after self-recovery), T18d (3-day after self-recovery), T22d (7-day after self-recovery), T25d (10-day after self-recovery and product treatment start), T32d (7-day after product treatment), T39d (14-day after product treatment) for all groups.
- **OCT:** standard facial scan will be done at T0 (baseline), T14d (after pretreatment), T15d (Timm post-procedure), T16d (1-day after self-recovery), T18d (3-day after self-recovery), T22d (7-day after self-recovery), T25d (10-day after self-recovery and product treatment start), T32d (7-day after product treatment), T39d (14-day after product treatment) for all groups.

Self-Assessment(N=60):

- **Self-Assessment Questionnaire on product efficacy** will be answered by subjects at T14d (after pre-treatment), T25d (10-day after self-recovery), T32d (7-day after product treatment), T39d (14-day after product treatment) for Group 1 (N=30);
- **Self-Assessment Questionnaire on cosmeticity** will be answered by subjects at T14d (after pre-treatment), T39d (after product treatment) for Group 1 (N=30).

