- Self-assessment questionnaire on post-procedure tolerance will be answered by subjects at T15d (Timm post-procedure), T16d (1-day after self-recovery), T18d (3-day after self-recovery), T22d (7-day after self-recovery), T25d (10-day after self-recovery) for all groups (N=60).

Test Duration:

9-visits in 39-days (7-days for washout, 14-days for pre-treatment, 1-day for Chemical procedure, 1-day self-recovery, 3-day self-recovery, 7-day self-recovery, 10-day skin self-recovery and 14-days post-treatment).

- Visit 1: T-7d
- Visit 2: T0 (baseline)
- Visit 3: T14d (14-day after pre-treatment)
- *Visit 4: T15d (Chemical procedure and Timm post-procedure)*
- Visit 5: T16d (1-day after self-recovery)
- Visit 6: T18d (3-day after self-recovery)
- Visit 7: T22d (7-day after self-recovery)
- Visit 8: T25d (10-day after self-recovery and product treatment start)
- Visit 9: T32d (7-day after product treatment)
- Visit 10: T39d (14-day after product treatment)

3. Selection of Volunteers

According to the declaration of Helsinki¹the subjects must consent to the study in writing. Before-hand they are informed about the study, its objectives, probable benefits, potential risks, and troublesome aspects, as well as about their rights and responsibilities. Volunteers, who fulfil the following criteria of inclusion and exclusion, take part in the study.

Inclusion Criteria:

Prospective subjects meeting all the criteria below will be eligible for enrolment:

- 1. Chinese women, 20-50 years old;
- 2. All skin types (dry, normal, oily and mixed);
- 3. No high risk of hyperpigmentation skin (adjusted by the Hyperpigmentation skin questionnaire refer to Annex 11.2);
- 4. Rough ad dull skin by self-declared;
- 5. Lack of radiance, brightness, smoothness by self-claimed;
- 6. Presenting with problems of acne mark, acne scar or blemishes on face;
- 7. Did not participate any clinical test or cosmetic product test on skin within 3 months;
- 8. Did not participate any chemical procedures for previous 2 months; and willing to not participate any procedures during the whole study;
- 9. No disagreement of dermatologist because of other reasons that exclude the participation of the volunteer.
- 10. In general good health at the time of the study;
- 11. Willing and able to participate as evidenced by signing of informed consent;
- 12. Willing and able to participate the assigned chemical procedure and apply the assigned products;

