5.5. Fractional Ultrapulse CO₂-laser

The Fractional Ultrapulse CO2-laser is a gas laser. It generates arrays which act on the dermis and promote the generation of dermal collagen and the rearrangement of collagen fibers. The instrument uses ultrapulse mode and the pulse ejects continuously or repeatedly with a frequency of 1000Hz. The Fractional Ultrapulse CO2-laser will be operated by medical technologist at T15d (Timm post-procedure).

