Evaluation visit on T14d

- a. Subjects wash face with usual cleanser, then pat dry with clean tissue paper at center.
- b. Acclimatization to the room condition for 30 minutes (the conditions with a well-controlled room temperature (21 ± 1 °C) and humidity ($45\%\pm5\%$).
- c. Clinical Assessment will be done by dermatologist for T14d.
- d. VISIA 7 will be done by trained technician for T14d.
- e. OCT scan will be done by trained technician for T14d.
- f. Corneometer will be done by trained technician for T14d.
- g. Vapometer will be done by trained technician for T14d.
- h. Cutometer will be done by trained technician for T14d.
- i. pH meter will be done by trained technician for T14d.
- j. LA sting test will be done by trained technician for T14d.
- k. Self-assessment questionnaire will be answered by subjects for T14d.
- l. The investigational products and standard products will be weighted and returned to subjects, meanwhile, the daily log will be also checked.
- m. Adverse Events/Local Intolerance will be checked and recorded

Chemical Procedure visit and Timme evaluation on T15d

- a. Subjects wash face with usual cleanser, then pat dry with clean tissue paper at center.
- b. One questionnaire should be answered by subjects.
- c. Pre-process of xxx for procedure preparation.
- d. CO2-laser will be done by medical technologist.
- e. Clinical Assessment will be done by dermatologist for Timm post-procedure.
- f. VISIA 7 will be done by trained technician for Timm post-procedure
- g. OCT scan will be done by trained technician for Timm post-procedure
- h. Corneometer will be done by trained technician for Timm post-procedure
- i. Vapometer will be done by trained technician for Timm post-procedure
- j. Cutometer will be done by trained technician for Timm post-procedure
- k. pH meter will be done by trained technician for Timm post-procedure
- 1. Adverse Events/Local Intolerance will be checked and recorded.

Evaluation visit on T16d (1-day after self-recovery)

- a. Clinical Assessment will be done by dermatologist for T16d.
- b. VISIA 7 will be done by trained technician for T16d.
- c. OCT scan will be done by trained technician for T16d.

- d. Corneometer will be done by trained technician for T16d.
- e. Vapometer will be done by trained technician for T16d.
- f. Cutometer will be done by trained technician for T16d.
- g. pH meter will be done by trained technician for T16d.
- h. Self-assessment questionnaire will be answered by subjects for T16d.

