Annex 11.3. Self-assessment Questionnaire

Answers given according to a 5-point scale: "5-completely agree 非常同意", "4-somewhat agree 比较同意""3-neither agree 说不上同意不同意", "2-somewhat disagree 比较不同意", "1-completely disagree 非常不同意"

Self-assessment - Pre-treatment	Yes/是	No/否	Comments/ 其他
术前 14 天产品使用问卷			, -
I feel skin is good prepared for procedure			
我觉得我的肌肤更强韧了,为特殊美容做好了准备			
I feel skin is comfort for procedure			
我觉得我的皮肤在特殊美容中更耐受了			
Skin feels intensively repaired			
肌肤感觉被深层修护			
I feel skin redness due to dryness is less occur?			
我感觉皮肤由于干燥而发红的情况减少了			
Skin feels strengthened			
肌肤感觉更强韧			
Skin feels hydrated			
肌肤感觉水润保湿			
Skin feels comfortable			
肌肤感觉舒服			
Skin feels smoother			
肌肤感觉更光滑			
Skin looks brighter			
肌肤看起来更明亮			
Skin looks more radiant			
肌肤看起来更有光泽			
Pores look less visible			
毛孔看起来不明显			
Skin feels more elastic			
肌肤感觉更有弹性			
Fine line looks less visible			
细纹看起来不明显			
Crow's feet wrinkle is reduced			
鱼尾纹看上去减少了			
Self-assessment - Recovery			
术前后 1 天,3 天,7 天,10 天恢复			
期问卷			
I feel pre-treatment with product help my skin recover fast			
after procedure			
我感觉提前14天使用产品,可以帮助肌肤在特殊美容后更			
快修复			
I feel pre-treatment with product help my skin recover			

		T
stable after procedure		
我感觉提前 14 天使用产品,可以帮助肌肤在特殊美容后更		
稳定		
I feel pre-treatment with product help my skin recover		
comfortable after procedure		
我感觉提前14天使用产品,可以帮助肌肤在特殊美容后更		
舒适		
I feel pre-treatment with product help my skin redness		
recovered		
我感觉提前14天使用产品,可以帮助肌肤在特殊美容后褪		
红		
I feel pre-treatmet with product help my skin dryness		
recovered		
我感觉提前14天使用产品,可以帮助肌肤在特殊美容后降		
低干燥爆皮		
I feel pre-treatment with product help my skin discomfort		
(e.g. red/dry/itch) from procedure recovered faster		
我感觉提前14天使用产品,可以使肌肤在特殊美容后的不		
适症状(如发红/干燥/瘙痒等)更快修复		
I would like to recommend my friends to use product before		
procedure		
我很乐意推荐我的朋友们,在特殊美容前使用产品		
I feel skin is comfort for procedure		
我觉得我的皮肤在特殊美容中更耐受了		
Self-assessment		
- Post-treatment		
术前7天及14天产品使用问卷		
Post-treat with product after skin recovered, skin feels		
smoother		
当肌肤在特殊美容恢复后,使用产品,肌肤感觉更光滑了		
Post-treat with product after skin recovered, skin feels		
brighter		
当肌肤在特殊美容恢复后,使用产品,肌肤感觉更明亮了		
Post-treat with product after skin recovered, skin feels		
more radiant		
当肌肤在特殊美容恢复后,使用产品,肌肤感觉更有光泽		
7		
Post-treat with product after skin recovered, skin pore is		
less visible		
当肌肤在特殊美容恢复后,使用产品,毛孔看起来不明显		
7		
Post-treat with product after skin recovered, skin feels		
more elastic		
当肌肤在特殊美容恢复后,使用产品,肌肤感觉更有弹性		

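### One item on the T14d pre-treatment questionnaire refers, in its Chinese text, to tolerance in a laser procedure given only on T15d, so its T14d result can express expectation but not procedural tolerance.

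*Protocol*

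**What the plan says.** Annex 11.3 has three blocks: pre-treatment, recovery and post-treatment. The heading of the first, in Chinese, describes it as the form on 14 days of product use before the procedure. It has 14 items. The second is printed as "I feel skin is comfort for procedure" in English and "我觉得我的皮肤在特殊美容中更耐受了" in Chinese. The same pair of lines is printed again as the last item of the recovery block, whose Chinese heading lists days 1, 3, 7 and 10.

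The product-efficacy questionnaire, for Group 1 only, "will be answered by subjects at T14d (after pre-treatment), T25d (10-day after self-recovery") and then at T32d and T39d (synopsis, section 4 and section 5.6). The T14d visit in section 7.2 repeats this: "Self-assessment questionnaire will be answered by subjects for T14d".

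The visit list under Test Duration gives "Visit 4: T15d (Chemical procedure and Timm post-procedure"). Section 5.5 agrees: "The Fractional Ultrapulse CO2-laser will be operated by medical technologist at T15d (Timm post-procedure"). In the T15d visit steps of section 7.2, step b is "One questionnaire should be answered by subjects" and step d is "CO2-laser will be done by medical technologist".

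Section 8.3.1 summarises each question by its mean or median, depending on a normality test, and also reports the share of ratings from 4 to 5.

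**The concern.** A woman completing the pre-treatment form at T14d has not yet had the laser. The Chinese item asks her to agree or disagree that her skin is more tolerant in the procedure. She can say what she expects, but she cannot report what happened.

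The analysis rule makes no exception for this item. Followed as written, the report would carry a T14d favourable-rating percentage under a label about procedural tolerance. Under section 6.2, Group 2 uses the same routine without a serum or a placebo serum, so Group 1 women can be taken to know that they are using the test product. Group 2 does not answer this questionnaire, so there is no control figure against which an expectation effect could be seen. Because the same words recur on the recovery form, a reader could also set the T14d and recovery percentages side by side as two measurements of one thing, when the first precedes the event.

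**Working it through.** No sample size, power or error rate is involved. The check compares days, the order of steps, and wording.

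**1. Day of the form against day of the laser.**
- Form: T14d (synopsis, section 4, section 5.6, section 7.2).
- Laser: T15d, once (Test Duration, study schedule, section 5.5, section 7.2).
- Laser day minus form day = 15 − 14 = 1 day. At T14d the number of respondents who have had the study procedure is 0.

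**2. Could the form belong to another visit?** The annex does not print a visit label on the block, so its link to T14d is inferred from the heading and the schedule. The only other candidate is the questionnaire at T15d. In section 7.2 that is step b and the laser is step d, so it too comes first. I find no reading of the schedule that puts this form after the laser.

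**3. Could the item refer to an earlier procedure?** Section 3 requires no chemical procedure in the previous 2 months (inclusion criterion 8), and exclusion criterion 17 rules out medical beauty treatment in the last 3 months. No recent procedure is available to be rated.

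**4. What the item asks.**

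| Version | Sense |
|---|---|
| Chinese | The skin has become more tolerant in the special beauty procedure. The construction 在…中 locates the tolerance in the procedure; 更…了 marks a change of state. |
| English | Comfort for a procedure; readiness for one to come is a possible reading. |
| Item directly above, both languages | The skin is prepared for the procedure. |

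Readiness already has its own item. The second item either duplicates it (English sense) or asks about something that has not occurred (Chinese sense).

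**5. Extent.**
- Items: 1 of 14, or 1/14 = 7.1% of the pre-treatment form.
- Respondents: every Group 1 woman who answers at T14d. The protocol plans at least 30 completers per group and enrols 70 in all. An equal split, which the protocol does not state, would give 70/2 = 35. The count is therefore at least 30 planned completers, and about 35 if all enrolled under that assumption respond.
- Analyses: the summaries of this item under section 8.3.1. The Group 1 versus Group 2 table in section 8.3.2 does not list the efficacy questionnaire.

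**The case against.** The best defence is that this is a clumsy readiness item and not a report of experience. It follows the preparedness item, its English leans the same way, and the final 了 marks a change of state, not a past tense. A woman can say at T14d that her skin now feels more tolerant. Much of this stands: it would be too strong to read the Chinese as an unmistakable report of a completed event, and part of the fault is a mismatch between the two languages. It does not save the T14d result as a measure of tolerance, because on the lenient reading too the answer is an expectation.

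A second defence is that little depends on the item. Post-procedure tolerance has its own questionnaire for both groups, scheduled from T15d to T25d, and the dermatologist grades erythema, edema, desquamation and other signs after the laser. No stated objective or group comparison rests on this one line. That also stands and limits the weight of the point.

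A reader might infer that the percentage is meant for an efficacy claim. Nothing in the protocol says so; it says only that the percentage is reported. A reader might also infer that exactly 30 answers are affected, but 30 is a minimum number of completers.

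Finally, the recovery form is not a perfect home for the item. The wording is comparative, and with one laser session a woman has no second procedure within the study to compare with. The days in the form's heading also do not match the efficacy schedule, which falls in the recovery period only at T25d. Each of those days is nevertheless after the laser, which is what matters here.

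**Conclusion.** The point holds as a minor fault in one questionnaire item. At T14d the item can record only expectation, its two language versions can be read differently, and section 8.3.1 as written would still give it a summary score and a favourable-rating percentage.

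The conclusion assumes that the pre-treatment block is the form used at T14d (or, at the latest, before the laser on T15d) and that the women answer the Chinese line. The first rests on the form's heading and the visit schedule; the second is likely in a study of Chinese women at a Shanghai site.

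It would be a mistake to infer that the study's assessment of tolerance is unsound, or that the comparison of the serum with no treatment is affected. The documents support neither: the fault is confined to the T14d use of one item in a Group 1-only questionnaire.

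**What to change.** Choose one of two changes to Annex 11.3 before the form is used:

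- **Delete** the item from the pre-treatment block. The cost is one T14d expectation rating.
- **Reword** the Chinese so that both languages ask about readiness or expectation, and label the result that way in the report. The cost is an item that largely duplicates the preparedness item above it.

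Either is sound; deletion is the simpler. In both cases, report no T14d result as procedural tolerance. Take that only from forms answered after the laser, where the recovery block already carries the identical item. If a T15d form is used for this purpose, it must be completed after the laser, not at step b of the T15d visit as section 7.2 now has it.

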5.6. Self-assessment Questionnaire (N=60)

- > Self-Assessment Questionnaire on product efficacy will be answered by subjects at T14d (after pretreatment), T25d (10-day after self-recovery), T32d (7-day after product treatment), T39d (14-day after product treatment) for Group 1 (N=30);
- ➤ **Self-Assessment Questionnaire on cosmeticity** will be answered by subjects at T14d (after pretreatment), T39d (after product treatment) for Group 1 (N=30).
- > Self-assessment questionnaire on post-procedure tolerance will be answered by subjects at T15d (Timm post-procedure), T16d (1-day after self-recovery), T18d (3-day after self-recovery), T22d (7-day after self-recovery), T25d (10-day after self-recovery) for all groups (N=60).

6. Product

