8.3. Efficacy Verification

8.3.1 Comparison between Time-points

A Shapiro-Wilk test will be used to test for normality of the baseline data (T0) and the change from baseline data (Tn-T0) at post-baseline time points at significance level alpha=0.01. When data passes normality (all normality of the distributions is confirmed for the same parameter), a parametric test will be used to test the null hypothesis that the mean change from baseline is zero. When data fails normality (if one or more normality of the distributions for the same parameter is rejected), a non-parametric test will be used.

Pre-treatment efficacy:

- a) T14d (after pre-treatment), T15d (Timm post-procedure) versus T0 (baseline)
- b) T16d (1-day after self-recovery), T18d (3-day after self-recovery), T22d (7-day after self-recovery), T25d (10-day after self-recovery) versus T15d (Timm post-procedure)

Post-treatment efficacy:

a) T32d (7-day after product treatment), T39d (14-day after product treatment) versus T25d (product treatment start)

The following will be calculated and reported for each evaluation parameter at applicable post-statistical baseline time point(s):

For self-assessment questionnaires, only the data of completing subjects will be analyzed. Questionnaire response options will be in the form of a 5-point semi-structured scale, ranging from one (1) to (5), where the score of one (1) will be the most negative/unfavorable rating and the score of five (5) will be the most positive/favorable rating the product can receive (the scale will also include a mid-point label "neither agree nor disagree"). Responses obtained for each question will be tested for normality using a Shapiro-Wilk test at significance level alpha=0.01, and if the data passes normality testing, mean scores will be used. Responses that are not normally distributed will be assessed using the median response. The percentage of ratings from

4 to 5 ("top XX box %") will be reported.

In the report appendices, raw data and open-ended questionnaire responses will be listed by subject. Data frequency and percentage will be presented for questionnaires and tolerability evaluations. Tolerability tables will also be sent to the Sponsor at the indicated interim data time points; SAQ data will be sent at study completion, for all completing subjects. Medians, means and percentage values will be reported to decimal place (0.0) for all questionnaire data.

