一元の1年197677日の久川・区川・田・地域へ80万円円	 	

	ı	
Post-treat with product after skin recovered, fine line looks		
less visible		
当肌肤在特殊美容恢复后,使用产品,细纹看起来不明显		
了		
Post-treat with product after skin recovered, crow's feet		
wrinkle is reduced		
当肌肤在特殊美容恢复后,使用产品,鱼尾纹看起来不明		
显了		
Post-treat with product after skin recovered, skin feels		
intensively repaired		
当肌肤在特殊美容恢复后,使用产品,肌肤感觉被深层修		
复		
Post-treat with product after skin recovered, skin feels		
strengthened		
当肌肤在特殊美容恢复后,使用产品,肌肤感觉更强韧了		
Post-treat with product after skin recovered, skin feels		
hydrated		
当肌肤在特殊美容恢复后,使用产品,肌肤感觉水润保湿		
Post-treat with product after skin recovered, skin feels		
comfortable		
当肌肤在特殊美容恢复后,使用产品,肌肤感觉舒适		
I would like to recommend my friends to use product for		
post-treat		
我很乐意推荐我的朋友们,在特殊美容后使用产品		

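### At T14d the Chinese pore and fine-line items ask about a state where the English claims a change, and the Chinese crow's-feet item is stricter after the laser than before it under the same English

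*Protocol*

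**What the plan says.** Annex 11.3 has a pre-treatment form (14 days of product use), a recovery form and a post-treatment form (7 and 14 days of product use). Each item is printed in English with a Chinese version below it.

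- **Pre-treatment, pores and fine lines.** The English is "Pores look less visible" and "Fine line looks less visible". The Chinese predicate in both is 看起来不明显, *look not noticeable*.
- **Post-treatment, pores and fine lines.** The Chinese is "当肌肤在特殊美容恢复后,使用产品,毛孔看起来不明显" and "当肌肤在特殊美容恢复后,使用产品,细纹看起来不明显". Both open with *after the skin has recovered from the procedure, using the product*, and both run on to a closing particle on the next line.
- **Crow's feet.** The English claims a reduction on both forms. The pre-treatment Chinese says 减少了, *have reduced*. The post-treatment Chinese is "当肌肤在特殊美容恢复后,使用产品,鱼尾纹看起来不明", continued on the next line by 显了: *no longer noticeable*.

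Section 5.6 gives the efficacy questionnaire to Group 1 only, at T14d and T25d and then at "T32d (7-day after product treatment), T39d (14-day after product treatment) for Group 1 (N=30"). It is not answered at T0. Section 8.3.1 says that "the score of five (5) will be the most positive/favorable rating the product can receive". It then reports a top-box figure: "The percentage of ratings from" 4 to 5.

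**The concern.** The study objective includes a comparison of the effect before and after use, so an efficacy item should capture a change. If the Chinese text asks about a state, agreement does not show that anything changed. Nothing in the design lets the starting state be removed afterwards: there is no T0 questionnaire, Group 2 does not answer these items, and the form has no answer for a woman who never had the problem. The inclusion criteria ask for self-declared roughness, dullness and lack of radiance, brightness and smoothness, and for acne marks, scars or blemishes. None requires visible pores, fine lines or crow's feet, and the age range is 20 to 50.

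What is at stake is the meaning of two T14d percentages and of the post-treatment crow's-feet percentages. If these are reported under their English labels, a reader will take them for something the respondents were not asked.

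**Working it through.** The protocol states no figure for these items, so there is nothing to reproduce. The check is a comparison of wording, followed by an illustration of size.

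**Wording, side by side**

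| Item | English | Chinese, pre-treatment | Chinese, post-treatment |
|---|---|---|---|
| Pores | change, both forms | state: 不明显, no 更, no 了 | change: frame *after using the product*, closing 了 |
| Fine lines | change, both forms | state: 不明显, no 更, no 了 | change: same frame, closing 了 |
| Crow's feet | reduction, both forms | change: 减少了 | change: 不明显了 (stricter) |

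Two notes on the reading:

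- In the text as read from the PDF, the closing particle of the post-treatment pore item appears as a stray 7. I take it as 了. The same character closes the radiance item on that form, and the parallel fine-line item shows 了 plainly.
- The pre-treatment form does mark change elsewhere: smoothness, brightness, radiance and elasticity carry 更, and crow's feet carries 减少了. Hydration and comfort are states in both languages, so they do not conflict. Pores and fine lines are the two appearance items where the English marks a change and the Chinese does not.

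**Size for the two T14d items**

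None of the following inputs is in the protocol except n = 30 (Group 1, Section 5.6):

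- q = share of women with no noticeable pores (or fine lines) at the start
- a = share of those women who agree with the state wording
- p = share of the remaining women who agree

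State wording: top box = q·a + (1 − q)·p. Change wording, if unaffected women do not agree: top box = (1 − q)·p. The excess is q·a, whatever p is.

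With a = 1 (the upper limit) and p = 0.3:

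| q | State wording | Change wording | Excess, women of 30 |
|---|---|---|---|
| 0 | 30% | 30% | 0 |
| 0.1 | 0.1 + 0.9 × 0.3 = 37% | 27% | 3 |
| 0.2 | 0.2 + 0.8 × 0.3 = 44% | 24% | 6 |
| 0.3 | 0.3 + 0.7 × 0.3 = 51% | 21% | 9 |
| 0.5 | 0.5 + 0.5 × 0.3 = 65% | 15% | 15 |

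If only half of the unaffected women agree (a = 0.5), the excess halves: at q = 0.2 it is 0.2 × 0.5 × 30 = 3 women.

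Change wording alone leaves the unaffected women in the denominator, where they cannot report a reduction. Leaving them out gives (1 − q)·p / (1 − q) = p, here 30% at every q above. The denominators become 27, 24, 21 and 15 for q = 0.1, 0.2, 0.3 and 0.5.

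**Crow's feet**

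A woman whose crow's feet have improved but can still be seen can agree with 减少了 and truthfully disagree with 不明显了. The post-treatment item therefore sets a higher bar than its English label. Both versions state a change, so the excess calculated above does not apply to this item.

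**The case against.** **The form's context may supply the change.** The pre-treatment form is headed as a questionnaire on 14 days of product use, and some women will read every item as before versus after. A woman without the problem could choose the scale's midpoint or write in the comments column. This stands as a reason not to assert an excess. It does not make the wording safe, because the literal answer to the Chinese item is agreement. The midpoint also helps only if the five-point scale is used; the printed columns are yes, no and comments.

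**The respondents' language is not stated.** That they answer from the Chinese is inferred from Chinese women enrolled at a Shanghai site. The protocol also does not say which language the report will use. Both are assumptions. If the report translated the Chinese literally, the label would be right, but the two items would still not measure a change.

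**q for pores may be small.** Entry requires rough skin and lack of smoothness by self-report, and the dermatologist's scale in Section 5.1 ties the worst pore grade to rough skin. This is fair, and large values of q are less plausible for pores. It says little about fine lines in women from age 20.

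**No comparison of T14d with T39d is planned.** Section 8.3.1 does not list one, and the two forms look back to different starting points. So the crow's-feet wording spoils no planned test. What remains is the mismatch with its own English label, and a trap for anyone who sets the two percentages side by side.

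**Little depends on these items.** They are absent from the between-group table in Section 8.3.2, and the dermatologist grades pores and crow's feet in both groups from T0. This stands, and it keeps the point minor.

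**Conclusion.** The point holds for two items at one visit and, on a different ground, for a third item. The T14d top-box percentages for pores and fine lines can include women who never had the problem. The excess is q·a, zero if there are no such women, and its actual size is unknown. It matters because there is no T0 answer and no Group 2 answer; in a randomised comparison of the same item the share q would be equal in expectation in both groups. The crow's-feet item asks a stricter question after the laser than before it, so the post-treatment percentage does not measure what its English label says.

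A reader might infer that all three items on both forms credit the serum to women who never had the problem. The documents do not support that: the post-treatment pore and fine-line items are framed by use of the product and close with 了, and both crow's-feet wordings state a change. Nor do they show that the T14d percentages will in fact be inflated; that is a risk created by the wording. The conclusion rests on the women answering from the Chinese text and on reading the stray character as 了. This is a small defect in the instrument that costs little to correct before use and cannot be repaired once answers are in.

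**What to change.** Before the forms are used:

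1. On the pre-treatment form, give the Chinese pore and fine-line items a comparative, for example 比使用前更不明显 (*less noticeable than before use*). The post-treatment versions need no change marker.
2. Use 减少了 for crow's feet on both forms, to match the English.
3. On both forms, add a did-not-have-this answer for pores, fine lines and crow's feet, referring to the start of that product period. State in Section 8.3.1 that these answers are left out of the denominator, and report how many there were.

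Do not restrict the denominator by the dermatologist's T0 grade instead. Pore grade 0 is defined as minimal visible pores and so does not mean absence, the reference for the post-treatment period is T25d, and a clinician's grade need not match what the woman notices.

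The cost is a few words on the forms, one answer option and one sentence in Section 8.3.1. The downside is a smaller denominator and possibly lower reported percentages for these items.
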